9.2.2. Drop-outs

Subjects who have not completed study visit on day 0 (start of intervention) and on day 35 (end of intervention) will be excluded from the analysis due to not being eligible for analysis of the primary endpoint.

Subjects who have used the weight vest less than 80% of requested time will be excluded from a possible additional per protocol analysis but not from the primary FAS analysis. Wearing time will be calculated as a mean of the total wearing time for the 5 weeks of intervention. Wearing time of 8 hours per day gives a total wearing time of 280 hours and subjects are thus required to wear the vest for at least 224 hours during the intervention period. This will be calculated after the end of intervention (day 35) based on self-reporting

Subjects who have been in a standing position (while wearing the weight vest) less than 80% of requested time will be excluded from a possible additional per protocol analysis but not from the primary FAS analysis. Standing time will be calculated as a mean of the total standing time for the 5 weeks of intervention. Standing time of 2 hours per day gives a total wearing time of 70 hours and subjects are thus required to be in a standing position for at least 56 hours during the intervention period. This will be calculated after the end of intervention (day 35) based on self-reporting

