5.5. Withdrawal criteria

Subjects can discontinue their participation in the study at any time without any consequence to further treatment. The subjects may be withdrawn from the study at the discretion of the investigator due to safety concerns or if judged non-compliant with study procedures. If the subject discontinues the study, follow-up of this subject will be performed according to the clinic's routine. In either case, serious adverse events will be followed up. Other reasons for discontinuing a subject are incorrect enrolment and subjects lost to follow-up.

All inclusion criteria must be fulfilled, and all exclusion criteria must not be fulfilled for all subjects throughout the whole study. If a subject is non-compliant with the protocol but still wishes to continue its participation in the study it is up to the investigator to judge the subjects possible continuation. This situation could for example occur if a subject temporarily is affected by illness

Study code:
Clinical Study Protocol

Version No:

Date: 2021-02-01

ATLAS

14.9

and therefore misses some of the study procedures. In case of a situation like this it is up to the investigator to judge further eligibility of the subject to continue the study.

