9. STATISTICS

9.1. Analysis population

The aim of this trial is to further elucidate the effect increased artificial loading has on body weight. It is important to identify if there is any effect of increased loading on obese subjects under optimal conditions and if all subjects are fully compliant to the study protocol. Therefore all participants that complete the study with regards to the primary outcome will be included in the analysis, e.g. analyses applicable to Full Analysis Set (FAS). A secondary per protocol analysis may be performed with regards to the study endpoints.

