These will be analyzed using the same methods as described for the primary endpoint. We will also compare absolute changes between the groups of individuals exposed to 11% and 1% artificial loading.

From the ANCOVA models adjusted for covariates, least square means (LSM) with 95 % confidence intervals will be calculated. P-values < 0.05 will be classified as significant. The p-values for within group comparison (5 weeks vs baseline) of the different parameters will be calculated using Wilcoxon signed rank-sum test.

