9.3. Sample size calculation

It is anticipated that a total of approximately 130 subjects are required to be screened to identify a statically significant (p<0.05) effect of 1.6% difference in relative body weight change between 5 weeks and baseline, when comparing high load with the low load group with 80% power. These calculations will allow a screening failure of 50% and a dropout rate of 20% after screening. Calculations are based on a standard deviation of 2% for change in body weight comparing 5 weeks with baseline. Power calculations demonstrate that a total of 25 evaluable participants per group are needed to significantly detect above mentioned effect size with a power of 80%.

Subjects will be screened and included in the clinical trial consequently until 25 subjects in the heavy weight vest group (intervention/high load group) and 25 subjects in the light weight vest group (control/low load group) are certain to complete the trial and be eligible for Full Analysis Set (FAS). Certainty will occur when that number of subjects have finished the intervention on day 35. Eligibility to Full Analysis Set (FAS) is defined as having completed the study visits on randomization (day 0) and at the end of intervention (day 35) and thus being eligible for assessment of the primary outcome. Screening and inclusion will probably be executed according to above mentioned calculations but could be adjusted along the timeline of the trial.

Study code: ATLAS
Version No: 14.9

Date: 2021-02-01

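### The set labelled Full Analysis Set contains completers only, so the primary weight comparison is not protected by randomisation and no day-35 weight is secured for those who leave

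*Protocol*

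**What the plan says.** Section 9.1 justifies the analysis population by the wish to see the effect under optimal conditions with full compliance. It concludes that "all participants that complete the study with regards to the primary outcome will be included in the analysis", and names this the Full Analysis Set. Section 9.2.2 states the rule from the other side: anyone lacking the day-0 or day-35 visit "will be excluded from the analysis due to not being eligible for analysis of the primary endpoint". Section 9.3 repeats the definition by attendance. Sections 5.4 and 9.3 keep recruitment open until 25 per arm have completed.

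The planning assumption in section 9.3 is: "These calculations will allow a screening failure of 50% and a dropout rate of 20% after screening".

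On people who leave, section 5.5 says: "If the subject discontinues the study, follow-up of this subject will be performed according to the clinic's routine". Section 8.3 adds an end-of-trial assessment for those removed from treatment, or withdrawing from it, because of an adverse event. It does not say what this contains or when it takes place.

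Body weight is measured at days 0, 15, 28, 35 and 49 (section 7.1.1.1). In section 9.2.1 the primary ANCOVA uses the change from day 0 to day 35. The day-15 and day-28 changes appear among the secondary endpoints, all of which are called exploratory.

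**The concern.** Membership of the primary analysis set depends on something that happens after randomisation. If the people who leave differ in weight response from those who stay, and do so differently by arm, the completers comparison is biased, and recruiting more people by the same process reproduces that bias. The label hides this, because a reader expects a Full Analysis Set to be close to everyone randomised.

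The stated rationale does not rescue the set. Section 9.2.2 keeps participants with low wearing or standing time in it, provided that they attend on day 35. It removes an adherent participant who misses that visit. The set therefore estimates neither the effect under full compliance nor the effect in all randomised participants.

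There is reason to expect load-related drop-out. Section 2.3 lists seven musculoskeletal items under high load and one under low load in the earlier three-week study. Section 4.1 says that potential participants are told the weight-loss hypothesis, so early non-response could also prompt leaving.

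**Working it through.** **1. The plan's own figures.** Inputs from section 9.3: a difference of 1.6 points ("effect of 1.6% difference in relative body weight change between 5 weeks and baseline"), an SD of 2 ("Calculations are based on a standard deviation of 2% for change in body weight comparing 5 weeks with baseline"), power 80% and alpha 0.05, taken as two-sided.

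n per arm = 2 × SD² × (1.960 + 0.842)² / difference² = 2 × 4 × 7.85 / 2.56 = 24.5, so 25. This reproduces the plan's 25 per group. Power at 25 per arm is 80.7% by the normal approximation and 79.1% by the noncentral t.

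**2. How many are lost.** 50 / 0.8 = 62.5, so 63 must enter, and 63 / 0.5 = 126 must be screened, in line with the plan's approximate 130. Forward: 130 × 0.5 = 65 enter and 65 × 0.8 = 52 complete. Either way about 13 are lost. The 20% is counted from screening (day -21) and randomisation is on day 0, so 13 is an upper figure for loss after randomisation at that rate.

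**3. Bias of the completers difference.** Let d be the share of an arm that drops out, and g the mean percent change of its drop-outs minus that of its completers (positive if drop-outs lose less weight). The all-randomised mean of an arm is its completers mean + d × g. The completers difference therefore overstates the high-load benefit by

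d(high) × g(high) − d(low) × g(low).

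The protocol gives neither d by arm nor g, so these values are assumptions. The standard error at 25 per arm is 2 × √(2/25) = 0.566.

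| d high / low | g high / low | Overstatement, points | Share of 1.6 | Two-sided type I error |
|---|---|---|---|---|
| 0.20 / 0.20 | 1.0 / 0 | 0.20 | 12.5% | 6.4% |
| 0.20 / 0.20 | 2.0 / 0 | 0.40 | 25% | 10.9% |
| 0.30 / 0.10 | 1.0 / 0 | 0.30 | 19% | 8.3% |
| 0.30 / 0.10 | 2.0 / 0 | 0.60 | 37.5% | 18.5% |
| 0.20 / 0.20 | 1.0 / 1.0 | 0 | 0 | 5.0% |

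**4. Simulation of drop-out driven by response.** All settings are assumed. SDs at days 15, 28 and 35 are 1.4, 1.8 and 2.0, with correlations 0.7 to 0.9. The true day-35 difference is -1.60, with half of it reached by day 15. The drop-out logit is -1.0 + b × (day-15 change), with b = 0.3, 0.6 or 0.9.

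- Rule in the high-load arm only (21% to 23% drop-out), low-load arm 10% at random: completers give -1.73, -1.82 and -1.89.
- Same rule in both arms (21% to 23% high, 28% to 32% low): completers give -1.57, -1.52 and -1.46.
- No true effect, rule in the high-load arm only (28% to 32% against 10%): completers give -0.15, -0.31 and -0.44, with type I error of about 6% to 12%.
- No true effect, same rule in both arms: about 0.

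An estimate that uses the day-15 weight returns about -1.60 (or 0 under no effect) in every case. It does so by construction, because drop-out was made to depend only on that weight.

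**5. A different quantity.** If 20% of the high-load arm get no effect and everyone is analysed, the difference is 1.6 × 0.8 = 1.28. With 25 / 0.8, about 31 per arm, power is about 70%; 80% needs 2 × 4 × 7.85 / 1.28² = 38.3, so 39 per arm. This is the effect in all randomised participants, not a measure of bias in the completers result.

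**The case against.** Several stronger readings suggest themselves, and the protocol does not support them.

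- **Interim weights go unused.** They are secondary endpoints; only the primary analysis ignores them.
- **Discontinuers are not weighed at day 35.** Section 5.5 concerns leaving the study, not taking off the vest, and section 9.2.2 keeps low wearers who attend. After adverse-event withdrawal, section 8.3 requires an assessment that might include a weight. A weighing is neither secured nor ruled out.
- **Most drop-outs have later weights.** The protocol gives no timing of drop-out. No weight is taken between day 0 and day 15, so a repeated-measures model has no later weight for anyone who leaves before then.
- **The benefit is overstated.** That needs drop-out to depend on response mainly in the high-load arm. With the same rule in both arms the sign reverses. The only drop-out evidence in the document is one musculoskeletal discontinuation per arm in the earlier study.

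These objections limit the claim without removing it. A separate analysis plan could add missing-data methods, but the protocol itself fixes both the exclusion and the definition of the set. The choice of a mixed model over other all-randomised methods is partly preference. The case for including all randomised participants does not depend on it.

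**Conclusion.** The point holds as a defect in the definition of the primary analysis set. The FAS is completers-only, its stated rationale does not describe it, and people who leave are made up by number. Up to about 13 of 63 to 65 entrants are affected at the planned rate.

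Bias is a risk of unknown direction. Under the assumed scenarios, completers give about -1.7 to -1.9 or about -1.5 to -1.6 against a true -1.60. With no true effect, a spurious -0.15 to -0.45 arises under the high-arm-only mechanism. Bias is zero if the product of drop-out share and gap is equal in the two arms. These figures rest on assumed drop-out rates, correlations and drop-out mechanisms; none comes from the protocol.

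The document also disagrees with itself on who is analysed. The abbreviations list defines ITT as randomised with at least 2.5 weeks of vest wear. Section 5.3 says that under-users will be excluded from the study, while section 9.2.2 keeps them in the FAS. Section 9.2.1 calculates values for all participating individuals.

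This should be settled before data are collected, because a day-35 weight that was never taken cannot be recovered.

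**What to change.** - Define the FAS as all randomised participants with a baseline weight, analysed by assigned arm. Call the present set completers.
- Take the primary estimate as the day-35 contrast from a likelihood-based repeated-measures model of percent weight change at days 15, 28 and 35, for example an MMRM with arm by visit and baseline covariates.
- Invite everyone who stops the vest or leaves early to the day-35 weighing already planned, unless consent is withdrawn.
- Keep the completers ANCOVA as a sensitivity analysis. Add one for data not missing at random, for example return to baseline, which also covers people who leave before day 15.
- Report the numbers randomised per arm beside the completers.
- Reconcile the abbreviations list and sections 5.3, 5.5, 8.3, 9.1, 9.2.1, 9.2.2 and 9.3 on who is followed and who is analysed.

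The cost is wording plus a few weighings, and possibly a smaller estimate. Participants who stopped the vest may dilute the difference, for example to 1.28, with about 70% power at 31 per arm. The protocol should therefore say that its 80% power applies to a 1.6-point difference.

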9.3. Sample size calculation

It is anticipated that a total of approximately 130 subjects are required to be screened to identify a statically significant (p<0.05) effect of 1.6% difference in relative body weight change between 5 weeks and baseline, when comparing high load with the low load group with 80% power. These calculations will allow a screening failure of 50% and a dropout rate of 20% after screening. Calculations are based on a standard deviation of 2% for change in body weight comparing 5 weeks with baseline. Power calculations demonstrate that a total of 25 evaluable participants per group are needed to significantly detect above mentioned effect size with a power of 80%.

Subjects will be screened and included in the clinical trial consequently until 25 subjects in the heavy weight vest group (intervention/high load group) and 25 subjects in the light weight vest group (control/low load group) are certain to complete the trial and be eligible for Full Analysis Set (FAS). Certainty will occur when that number of subjects have finished the intervention on day 35. Eligibility to Full Analysis Set (FAS) is defined as having completed the study visits on randomization (day 0) and at the end of intervention (day 35) and thus being eligible for assessment of the primary outcome. Screening and inclusion will probably be executed according to above mentioned calculations but could be adjusted along the timeline of the trial.

Study code: ATLAS
Version No: 14.9

Date: 2021-02-01

10. QUALITY CONTROL AND QUALITY ASSURANCE

10.1. Quality Assurance and Oversight

The PI is responsible for assuring that all study personnel involved in the are properly trained before getting involved in any study specific procedures or meet any study participants. Training of study personnel will be carried out through reading of the latest version of the study protocol, meetings or other documents provided by the PI. The training can be received directly from the PI or other trained study personnel after delegation from the PI. Working manuals for study specific procedures will be provided to minimize errors or inconsistency at study visits.

The PI shall allow study-related monitoring, auditing, and regulatory inspections by providing direct access to the CRF, paper print out from medical record, as well as other source data and other study-specific documentation. This shall also be apparent to the subjects in the Subject Information and Informed Consent form.

The sponsor shall construct a study monitoring plan which will be based on the identified risks, as well as follow-up of risks during the study.

10.2. Monitoring

The study will be monitored by an independent monitor before the study begins, during the study conduct, and after the study has been completed, so as to ensure that the study is carried out according to the protocol and that data is collected, documented, and reported according to ICH-GCP and applicable ethical and regulatory requirements. Monitoring is performed as per the study's monitoring plan and is intended to ensure that the subject's rights, safety, and well-being are met as well as data in the CRF are complete, correct, and consistent with the source data.

A study monitor will be appointed by the sponsor. The monitor will be appropriately trained and informed about the nature of the study, subject written information, GCP and applicable regulatory requirements.

The monitor will have regular contacts with the clinic to verify informed consents of participating subjects, to confirm that facilities remain acceptable, that the investigational team is adhering to the protocol, that data are being accurately recorded in the CRFs, to verify inclusion/exclusion criteria, study main endpoints, check AE/SAE reporting and that therapy accountability is being carried out. The investigator should ensure that all persons assisting with the trial are adequately informed and trained about the protocol, the investigational products(s) and their trial related duties and factions. The monitor will check that training has been performed and that this is documented. The monitor will also ensure source data verification (comparison of the data in the CRF with the medical records and other source data). The monitor must have direct access to source data. The extent of monitoring will be defined in a monitoring plan.

10.3. Source Data

The investigator must keep source documents for each subject in the study. A document describing what has been classified as source data in the study, a source data log, should be included in the Investigator Site File (ISF). The investigator must ensure that all source documents are accessible for monitoring and other quality control activities. The CRF is defined as source data in this study.

Study code: ATLAS
Version No: 14.9

Date: 2021-02-01

10.4. Deviations or serious breaches

Serious breaches and deviations from the study protocol, GCP and other regulations that significantly and directly affects, or with high likelihood could affect, the subjects or the scientific value of the study, shall be immediately reported within 7 days (from knowledge) to the PI. It is the PI's responsibility to judge the consequences of deviations that have occurred, and thus also to decide whether any Swedish Authorities should be informed.

Minor deviations that do not affect subjects' integrity or safety, nor significantly affect the study's scientific value, are documented in the study documentation of the principal investigator and the PI.

10.5. Audits and inspections

Authorized representatives of the PI, a Competent Authority or an Ethics Committee may perform audits or inspection at the center, including source data verification. The investigator must ensure that all source documents are accessible for auditing and inspection. The purpose of an audit or inspection is to systematically and independently examine all study-related activities and documents, to determine whether these activities were conducted, and data were recorded, analyzed and accurately reported according to the protocol, Good Clinical Practice (GCP) and any applicable regulatory requirements.

11. ETHICS

11.1. Compliance to the protocol, GCP and regulations

The study will be performed in compliance with the study protocol, the Declaration of Helsinki, ICH-GCP (Good Clinical Practice) guidelines and current national and international regulations governing this clinical trial. This is to ensure the safety and integrity of the study subjects as well as the quality of the data collected.

11.2. Ethical review of the study

The final study protocol for clinical trials must be approved, as a part of the application for a permit for clinical trials, by the Swedish Ethical Review Authority (Etikprövningsmyndigheten, EPM) before the trial can be conducted. The final version of the informed consent form and other information provided to subjects, must be approved or given a written positive opinion by EPM. EPM must be informed of any changes in the study protocol in accordance with current requirements.

11.3. Procedure for obtaining informed consent

The principal investigator shall ensure that the subject is given full and adequate oral and written information about the study, its purpose, any risks and benefits as well as inclusion and exclusion criteria. Subjects must also be informed that they are free to discontinue their participation in the study at any time without having to provide a reason. Subjects should be given the opportunity to ask questions and be allowed time to consider the provided information.

If the person chooses to participate, both the subject and the investigator shall sign the informed consent form. A copy of the subject information as well as the informed consent form shall be provided to the subject. The subject's signed and dated informed consent must be obtained before performing any study-specific activity in the study. Each subject who participated in the study will be identified by a subject number on a subject identification list. The subject agrees that monitors, auditors, and inspectors may have access to their medical records and other source data. If new information is added to the study, the subject has the right to reconsider whether he/she will continue their participation.

Study code: ATLAS
Version No: 14.9

Date: 2021-02-01

11.4. Subject data protection

If any part of the data is handled by any other organization, inside or outside the EU, appropriate agreements and/or other documentation will be established, to ensure that the data processing is performed in accordance with the provisions of the General Data Protection Regulation (GDPR) and other relevant legislation, before any data transfer takes place.

The content of the informed consent form complies with relevant integrity and data protection legislation. In the subject information and the informed consent form, the subject will be given complete information about how collection, use and publication of their study data will take place. The subject information and the informed consent form will explain how study data are stored to maintain confidentiality in accordance with national data legislation in a computer database. All information processed by the PI will be pseudonymized and identified with a study code.

The informed consent form will also explain that for verification of the data, authorized representatives of the PI, as well as relevant authority, may require access to parts of medical records or study records that are relevant to the study, including the subject's medical history.

